3.3 Study Randomization, Stratification, or Description of Non-Random Assignment Procedures

Adolescents will be randomized in a 1:1:1 ratio into 1 of the 3 consent conditions using block randomization with block size k=3 (so that in every 3 subjects, exactly 1 is allocated to each condition). The randomization will be stratified by study site and sex assigned at birth. Within study site, sex assigned at birth, and consent condition, the order in which the hypothetical trials will be presented to adolescents will be block randomized with block size k=2.

Enrollment of parents will be restricted to approximately 15 parents of adolescent natal males and 15 parents of natal adolescent females at each study site. Parents will indicate the acceptability of each of the three consent conditions for each of the two hypothetical trials. Independently of the gender strata, the order of hypothetical trial presentation will be block randomized with blocks size k=2. Separately for each hypothetical trial, the order of evaluation for the three consent conditions will be randomized so that each ordering is equally likely.

A subset of 6-8 adolescents (3-4 natal males and 3-4 natal females) and 6-8 parents of adolescents (3-4 parents of natal males and 3-4 parents of natal females) at each site will be selected for participation in the debriefing interview. All study participants will be asked if they are willing to participate in the debriefing interview until quotas have been reached.

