MTN	Microbicide Trials Network
NICHD	National Institute of Child Health and Development
NIDA	National Institute on Drug Abuse
NIMH	National Institutes of Mental Health
NIST	National Institute of Standards and Technology
OHRP	Office of Human Research Protection
PAMAB	Pediatric, Adolescent, and Maternal AIDS Branch
PGP	Pretty Good Privacy
PI	Principal Investigator
PrEP	Pre-exposure prophylaxis
QA	Quality Assurance

QNS	Query and Notification System
RS	Research Staff
SID	Study Identification Number
SIS	Study Information Sheet
SMC	Study Monitoring Committee
STI	Sexually transmitted infection
STRC	Study Team Review Committee
TDF-FTC	tenofovir-emtricitabine
UBACC	UCSD Brief Assessment of Capacity to Consent
UCSD	University of San Diego
UE	Untoward Event
US	United States
WTP	Willingness to Participate
WTS	Willingness to Support
YMSM	Young men who have sex with men
YWSM	Young women who have sex with men

STUDY ABSTRACT

DESIGN:

This study will use CASI completed by all participants and a detailed debriefing interview completed for a subset of participants to assess high-risk minor adolescents' willingness to participate in and parents willingness to support their teen's participation in two hypothetical trials using simulated consent processes. The two hypothetical trials are modeled after ATN 113 and HPTN 077.

The purpose of this study is to examine how the consent process affects the acceptability of participation in biomedical HIV prevention trials, from the perspective of behaviorally high-risk minors and the parents of minor adolescents.

DURATION:

Study participation will last approximately 60 minutes on a single day with no follow-up. Participants who agree to participate in the debriefing interview will require an additional 45 minutes immediately following the completion of the main study procedures.

SAMPLE SIZE :

Approximately 144 (36 per study site) high-risk minor adolescents and 144 (36 per study site) parents of adolescents will be recruited for participation in this study. Of note, the adolescents and parents will not be parent-child dyads; they will be unrelated. A subset of 24-32 (6-8 per study site) adolescents and 24-32 (6-8 per study site) parents will be selected to participate in the debriefing interview.

POPULATION:

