3.2 Sample Size

This study will enroll approximately 144 (36 per study site) high-risk minor adolescents and 144 (36 per study site) parents of adolescents. A subset of 24-32 (6-8 per study site) adolescents and 24-32 (6-8 per study site) parents will be selected to participate in the debriefing interview. Of note, the adolescents and parents will not be parent-child dyads; they will be unrelated. We project total enrollment of 288 participants, however, since this is a multi-site project with simultaneous recruitment with a hard to reach population, we may schedule and enroll more subjects than anticipated.

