To avoid the accidental inclusion of parent-child dyads, we will ask each participant to give the first 5 digits of their street address and first 4 characters of apartment/unit, where applicable. For example, if someone lived at 1234 Main Street Apt. 408, the value for that address would be 01234408. The value will be labeled “Family ID” and stored only until the end of the enrollment period. Once the site has filled all quotas, the Family ID will be permanently deleted. The RS will receive an email from Qualtrics indicating the participant’s eligibility. If the participant is eligible based on the screening questionnaire, the RS will use the Family ID Report in Qualtrics to identify any matching Family IDs. If there is no match, the participant qualifies and can begin the study. All eligibility requirements are assessed without the PI’s input. If interested, the adolescent will either: 1) provide contact information to arrange the study visit or 2) complete the study procedures the same day as s/he was screened. Eligible participants will be invited to participate in an on-site debriefing interview (until quota is filled), immediately following the final CASI.

4.3.2 Parents or guardians:

This study will recruit 36 parents/guardians at each site. Parents will be recruited primarily through contact in the clinical setting. If recruitment is slow, we will begin using advertising on social media (Facebook, Twitter), the LGBTQ youth centers referenced above, and through the local chapters of Parents, Families, and Friends of Lesbians and Gays, as well as churches, and other social settings familiar to our target audience. Parents recruited in person will complete the questionnaire on a tablet on the same day they are recruited. Parents who self-refer or hear about the study from friends will need to complete the screening questionnaire online.

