To avoid the accidental inclusion of parent-child dyads, we will ask each participant to give the first 5 digits of their street address and first 4 characters of apartment/unit, where applicable. For example, if someone lived at 1234 Main Street Apt. 408, the value for that address would be 01234408. The value will be labeled “Family ID” and stored only until the end of the enrollment period. Once the site has filled all quotas, the Family ID will be permanently deleted. The RS will receive an email from Qualtrics indicating the participant’s eligibility. If the participant is eligible based on the screening questionnaire, the RS will use the Family ID report in Qualtrics to identify any matching Family IDs. If there is no match, the participant qualifies and can begin the study. All eligibility requirements are assessed without the PI’s input. If interested, the parent participant will either: 1) provide contact information to arrange the study visit or 2) complete the study procedures the same day as s/he was screened. Eligible participants will be invited to participate in an on-site debriefing interview (until quota is filled), immediately following the final CASI.

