5.2.2. Parent Participants

Enrollment of parents will be restricted to approximately 18 parents of adolescent natal males and 18 parents of natal adolescent females at each study site. Parents will indicate the acceptability of each of the three consent conditions for each of the two hypothetical trials. Independently of the gender strata, the order of hypothetical trial presentation will be block randomized with blocks size k=2. Separately for each hypothetical trial, the order of evaluation for the three consent conditions will be randomized so that each ordering is equally likely.

A subset of 6-8 parents at each site will be selected using quota sampling for participation in the debriefing interview. Participants will be asked if they are willing to participate in the debriefing interview unless the quota for their demographic group has been reached.

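### The parent quota of 15 + 15 per site in the abstract and Section 3.3 gives 120 parents and contradicts the 18 + 18 per site in Section 5.2.2 and the stated total of 144.

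*Combined protocol and SAP*

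**What the plan says.** Two places set the lower quota. The Randomization paragraph of the abstract and Section 3.3 both state that parent enrollment is "restricted to approximately 15 parents of adolescent natal males and 15 parents of natal adolescent females at each study site".

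The other places that give a parent count agree on a higher one:

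- Section 5.2.2 has the matching sentence with different numbers: "restricted to approximately 18 parents of adolescent natal males and 18 parents of natal adolescent females at each study site".
- The abstract, under Sample Size: "144 (36 per study site) parents of adolescents will be recruited for participation in this study".
- Section 3.2: "This study will enroll approximately 144 (36 per study site) high-risk minor adolescents and 144 (36 per study site) parents of adolescents". It adds: "We project total enrollment of 288 participants".
- Section 4.3.2: "This study will recruit 36 parents/guardians at each site".

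The abstract therefore disagrees with itself, between its Sample Size and Randomization paragraphs. Section 3.2 allows for a departure from the projection in one direction only: "we may schedule and enroll more subjects than anticipated".

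**The concern.** The sentence is worded as a restriction, so it tells a site when to close each stratum of parents. Section 3.3 is also where Section 10.1 sends the reader, twice, for the randomization details. A site working from Section 3.3 closes at 30 parents; a site working from Section 5.2.2 closes at 36. If sites differ, the number of parents per site becomes unequal by accident. If all follow Section 3.3, the study misses its stated parent sample size.

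There is a second, conditional effect. Section 4.3.2 says: "Once the site has filled all quotas, the Family ID will be permanently deleted". Suppose a site takes 30 as its parent quota, has filled its other quotas and deletes the Family IDs. It could not then check 6 later parents against enrolled adolescents, as criterion 4.2.3 requires.

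**Working it through.** **Inputs.** Four sites (Section 4.3). Parents per site: 36 (abstract, Sections 3.2 and 4.3.2), 18 + 18 (Section 5.2.2), or 15 + 15 (abstract and Section 3.3). Adolescents: 144 (Section 3.2). Projected total: 288 (Section 3.2).

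**The plan's own figures.** 36 × 4 = 144 parents, as stated. 144 adolescents + 144 parents = 288, as stated.

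**The two restrictions.**

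| | 18 + 18 (Section 5.2.2) | 15 + 15 (abstract, Section 3.3) |
|---|---|---|
| Parents per site | 36 | 30 |
| Parents, four sites | 36 × 4 = 144 | 30 × 4 = 120 |
| Parents per child-sex stratum | 18 × 4 = 72 | 15 × 4 = 60 |
| Total with 144 adolescents | 288 | 264 |

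Only the 18 + 18 column reproduces 144 and 288.

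**Shortfall.** Per site: 36 − 30 = 6, or 3 in each stratum. Over four sites: 144 − 120 = 24, and 24/144 = 16.7%.

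**Effect on precision.** Taking interval width as proportional to 1/√n:

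- All four sites stop at 30: √(144/120) = 1.095, about 9.5% wider. The ratio is the same within a child-sex stratum: √(72/60) = 1.095.
- One site stops at 30: 144 − 6 = 138 parents, and √(144/138) = 1.02, about 2% wider.

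**Does the 120 in Section 10.3 support 15 + 15?** No. That figure is for adolescents, 40 in each of three consent conditions, whereas every parent rates all three conditions. Section 10.3 gives no parent sample size. Its calculation is sound for 120. I used an F test with 2 numerator degrees of freedom, 120 − 7 − 1 = 112 denominator degrees of freedom, f² = 0.09 and α = 0.05. Power is 0.82 to 0.84, depending on the noncentrality convention, and the f² detectable with 80% power is 0.083 to 0.086, consistent with the stated 0.09. With the planned 144 adolescents, power at f² = 0.09 is 0.89 to 0.90. Section 10.3 is therefore conservative and not in error.

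**The case against.** The strongest reply is that little depends on the discrepancy. Section 10.3 justifies the parent sample only by comparison with the adolescent calculation at 120, adding that the parent comparison is within-participant. With 120 parents that argument is unchanged. This stands: the cost is in precision, and the full 9.5% arises only if every site stops at 30.

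A silent stop at 30 may also be unlikely. The procedural text (Section 5.2.2) and the recruitment text (Section 4.3.2) both lead to 36, the Study Team Review Committee sees enrollment reports at least monthly, and sites can raise queries. This makes the error less likely to do harm, but leaves two incompatible restrictions in the current text.

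The word "approximately" does not reconcile them. It stands before both 15 and 18 in otherwise matching sentences, and 30 is 16.7% below 36. The allowance in Section 3.2 for extra enrollment does not help either, since it concerns going above the projection.

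The Family ID effect needs several steps in sequence. Section 4.3.2 also says that the ID is kept until enrollment ends, and a site still due to enroll parents has arguably not reached that point. For any one site, ending 6 short and reopening without IDs are alternatives, not cumulative harms. The effect is therefore a possibility that adds a reason to correct the text, and the case does not depend on it.

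**Conclusion.** The contradiction is real. The 15 + 15 restriction in the abstract and Section 3.3 cannot be applied together with the 18 + 18 in Section 5.2.2, and it does not produce the stated 144 parents or 288 participants. At most the study loses 24 parents (16.7%), with intervals for parent estimates about 9.5% wider. That assumes all four sites stop at exactly 30 and that interval width scales with 1/√n. Each site that follows Section 3.3 costs 6 parents. No power statement in the plan is undermined. The point deserves correction because the wrong number sits in an operative enrollment rule and is cheap to put right.

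**What to change.** Change 15 and 15 to 18 and 18 in the Randomization paragraph of the abstract and in Section 3.3. Both would then agree with the abstract's sample size and with Sections 3.2, 4.3.2 and 5.2.2. The documents do not say where the 15 came from, so the sponsor should confirm that 36 parents per site is intended. The cost is two reworded sentences, with no participants beyond the 144 parents already stated.

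Optionally, and not as a correction, Section 10.3 could say why it uses 120 adolescents when 144 are planned.

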3.4 Outcome Measures

3.4.1 Adolescents' Willingness to Participate (WTP) Scores

Adolescents' WTP will be used to measure the acceptability of biomedical HIV prevention trials from the perspective of high-risk minor adolescents. Adolescent WTP is measured using the question "If offered the chance, how likely would you be to participate in the study?" with response options ranging from "definitely not participate" to "definitely participate". The adolescent WTP will be measured after each of the two simulated study consent is completed, resulting in two WTP scores per adolescent.

3.4.2 Parents' Willingness to Support (WTS)

We use a number of measures to assess WTS a minor adolescent's participation in the study. The most obvious way to assess WTS is to ask the parent whether s/he would grant permission for his/her teenager to enroll in the study. However, this question can only be asked after the scenario in which parental permission is required because in the other two scenarios parental permission is either optional or not solicited, rendering the parent's preferences about participation moot. Thus, WTS includes not only projected likelihood of granting permission to join the study, but also: (1) a measure of the extent to which the parent finds the vignette's consent scenario an acceptable process for enrolling his/her adolescent; (2) measures of the parent's perception of his/her adolescent's capacity to consent to the two studies in question; (3) a measure of the parent's expectation that his/her adolescent would discuss the study prior to enrollment, even if such a discussion were not required; (4) a measure of the likelihood a parent would allow his/her adolescent to join the study. In summary, after each vignette the parent will answer two or three Likert-type questions that together will be used to assess WTS.

3.4.3 University of San Diego Brief Assessment of Capacity to Consent (UBACC) Scores

The UBACC will be administered to all participants. The UBACC includes ten open-ended questions to measure participant's understanding of research design, risks and benefits, and voluntariness. Each of the ten items are given a score of 0 indicating "a clearly incapable response", 1 indicating uncertainty or a partially appropriate, or 2 indicating "a clearly capable response". The UBACC will be completed for each of the two simulated studies, resulting in two UBACC scores per participant.

3.4.4 Qualitative Debriefing Interviews

The debriefing interview is a 30-45 minute interview designed to explore adolescent and parent perspectives on the various consent conditions in greater depth, and to better understand the role of study features, family, and adolescent characteristics in willingness to participate/willingness to support the hypothetical research studies. At the start of the interview, the participants will be informed that the interview will be recorded and transcribed and the participant will be asked to select a pseudonym for the researchers to use. The adolescent debriefing interview will consist of five sections including (1) general opinions about participating in HIV prevention studies, (2) opinions on the two specific studies, (3) relationship to parents, (4) opinions about parental involvement in the consent process, and (5) options/opinions for consenting in future studies. The parent debriefing interview will consist of four section including (1) general opinions about HIV prevention studies, (2) relationship to their teenager, (3) opinions about parental involvement in the consent process, and (4) options/opinions for consenting in future studies.

4.0 SELECTION AND ENROLLMENT OF STUDY PARTICIPANTS

4.1 Adolescent Inclusion Criteria

To be considered eligible for enrollment, an adolescent must meet all the criteria listed below.

4.1.1 Age 14-17 inclusive; and

4.1.2 Able to read and speak English; and

4.1.3 HIV status is negative or unknown; and

4.1.4 Engaged in high-risk sexual activity (**Table 1**) in the last 12 months; and

4.1.5 Not the child of a parent already enrolled in the study.

4.2 Parent Inclusion Criteria

To be considered eligible for enrollment, a parent must meet all the criteria listed below.

4.2.1 Able to read and speak English; and

4.2.2 Parent or guardian of an adolescent who is between ages 14-17; and

4.2.3 not the parent of a child already enrolled in the study.

Table 1. Criteria for high-risk sexual behavior

High-risk sexual behavior criteria for natal males	High-risk sexual behavior criteria for natal females
During the last 12 months, which of the following is true for you? (check all that apply): 
• I had unprotected anal sex with a male• I had protected anal sex with 3 or more males• I had sex with a male for money, gifts, shelter, or drugs	During the last 12 months, which of the following is true for you? (check all that apply): 
• I had unprotected anal or vaginal sex with a male• I had sex with someone who is HIV+• I had protected vaginal or anal sex with 3 or more males

• I had sex with a male, and I have had a sexually transmitted infection (gonorrhea, chlamydia, syphilis, herpes)• I had sex with someone who is HIV+• I had anal sex with a male and the condom slipped off or broke• None of the above	
• I had sex with a male for money, gifts, shelter, or drugs• I have had sex with one or more males, and I have had a sexually transmitted infection (gonorrhea, chlamydia, syphilis, herpes)• I had vaginal or anal sex with a male and the condom slipped off or broke• None of the above
---	---

4.3 Recruitment and Screening

This study will recruit adolescents between ages 14-17, inclusive, and parents of adolescents in the same age range. Participants will be recruited from four partnering research sites in the following U.S. cities: Baltimore, MD (partnering organization: Johns Hopkins University, partnering researcher: [name]), Chicago, IL, (partnering organization: University of Chicago, partnering researcher: [name]), Denver, CO (partnering organization University of Colorado, partnering researcher: [name]), and Tampa, FL (partnering organization University of South Florida, partnering researcher: [name]).

Specific recruitment procedures for each group are described in detail below.

4.3.1 Adolescents aged 14-17:

This study will recruit 36 adolescents at each site primarily through contact in the clinical setting. If recruitment is slow, we will begin using advertising on social media (Facebook, Twitter, chat services); support centers for lesbian, gay, bisexual, transgender, and questioning (LGBTQ) youth; churches and other social settings (e.g. Gay Straight Alliance at local high schools) and at clinics affiliated with the partnering organization. All interested adolescents will complete a screening questionnaire that should take about 10 minutes to complete.

Adolescents recruited in person will complete the questionnaire on a tablet on the same day they are recruited. Adolescents who self-refer or hear about the study from friends will need to complete the screening questionnaire online. All eligible adolescents will provide contact information regardless of recruitment and screening method.

To avoid the accidental inclusion of parent-child dyads, we will ask each participant to give the first 5 digits of their street address and first 4 characters of apartment/unit, where applicable. For example, if someone lived at 1234 Main Street Apt. 408, the value for that address would be 01234408. The value will be labeled “Family ID” and stored only until the end of the enrollment period. Once the site has filled all quotas, the Family ID will be permanently deleted. The RS will receive an email from Qualtrics indicating the participant’s eligibility. If the participant is eligible based on the screening questionnaire, the RS will use the Family ID Report in Qualtrics to identify any matching Family IDs. If there is no match, the participant qualifies and can begin the study. All eligibility requirements are assessed without the PI’s input. If interested, the adolescent will either: 1) provide contact information to arrange the study visit or 2) complete the study procedures the same day as s/he was screened. Eligible participants will be invited to participate in an on-site debriefing interview (until quota is filled), immediately following the final CASI.

4.3.2 Parents or guardians:

This study will recruit 36 parents/guardians at each site. Parents will be recruited primarily through contact in the clinical setting. If recruitment is slow, we will begin using advertising on social media (Facebook, Twitter), the LGBTQ youth centers referenced above, and through the local chapters of Parents, Families, and Friends of Lesbians and Gays, as well as churches, and other social settings familiar to our target audience. Parents recruited in person will complete the questionnaire on a tablet on the same day they are recruited. Parents who self-refer or hear about the study from friends will need to complete the screening questionnaire online.

To avoid the accidental inclusion of parent-child dyads, we will ask each participant to give the first 5 digits of their street address and first 4 characters of apartment/unit, where applicable. For example, if someone lived at 1234 Main Street Apt. 408, the value for that address would be 01234408. The value will be labeled “Family ID” and stored only until the end of the enrollment period. Once the site has filled all quotas, the Family ID will be permanently deleted. The RS will receive an email from Qualtrics indicating the participant’s eligibility. If the participant is eligible based on the screening questionnaire, the RS will use the Family ID report in Qualtrics to identify any matching Family IDs. If there is no match, the participant qualifies and can begin the study. All eligibility requirements are assessed without the PI’s input. If interested, the parent participant will either: 1) provide contact information to arrange the study visit or 2) complete the study procedures the same day as s/he was screened. Eligible participants will be invited to participate in an on-site debriefing interview (until quota is filled), immediately following the final CASI.

